10.3 Safety Oversight

The Data Safety Monitoring Board, DSMB, will function as an independent oversight committee charged with overseeing participant safety and providing recommendations to the PI and Georgetown University regarding the continuing conduct of the study. The DSMB will review periodic blinded Interim Safety Reports. Additionally, unblinded but sealed Interim Safety Reports will be provided to each voting DSMB member should the committee determine that review of unblinded safety data is warranted.

The DSMB is responsible for monitoring the tolerability, safety and effectiveness of the yogurt. They will meet periodically once the first participant is enrolled and continue to do so as long as participants are actively involved in the study. One meeting will occur before enrollment to review study objectives, data collection and safety measures. Meetings will occur via teleconferences or at Georgetown University.

11 STATISTICAL AND LABORATORY ANALYSES

11.1 STUDY HYPOTHESES

Hypothesis 1: Children receiving antibiotics who receive the yogurt with BB-12 will demonstrate less diarrhea than those receiving a control yogurt without BB-12.

Hypothesis 2: Yogurt containing BB-12 will be safe and well tolerated in this larger pediatric population. This is a Phase II trial that requires additional testing to further evaluate the safety of high dose BB-12.

11.2 SAMPLE SIZE CONSIDERATIONS

Sample Size Calculation for the Primary Outcome: This study is a double blinded, randomized Phase II trial where subjects will be randomly assigned (1:1) to either a probiotic (BB-12) yogurt group or to a control yogurt group. The primary outcome is dichotomous, clinically diagnosed diarrhea or no diarrhea, with the rate of AAD in the general population estimated to be 20-35%. Preliminary results from the Cochrane review showed the incidence of AAD in a high dose probiotic group to be 8% versus 22% in a control group.[108] Using the Cochrane estimates, a total sample of 300 subject (150 per group) would provide a power of 0.92 for detecting a difference of 0.14 (0.22 control - 0.08 probiotic) at alpha = 0.05, 2-tailed. To allow for one interim analysis (at approximately 50% recruitment), and then adjusting the final p-value to 0.029, the power would still be 90% for detecting the difference of 0.14 in the rates of AAD. If the difference in the final rates is smaller than 0.14, such as 0.12, the resulting power would still be sufficiently large (80%) and power would be equal to 74% if the final difference in rates were equal to 0.10. While the hypothesis is one-sided (see Aim 1; we expect children receiving probiotic intervention will demonstrate less AAD than those receiving the control product), we still used a two-tailed alternative for estimating the sample size in order to be conservative. While multiple efforts are arranged to minimize loss of data, in order to obtain the primary outcome (diarrhea or no diarrhea), there still will be some participants lost to follow-up and the endpoint is unknown. Nonetheless, if the lost to follow-up rate is as high as 10% (then N=270, approximately 135 per group), power would still be 90% for detecting the difference of 0.14 and 80% for detecting a difference of 0.12.

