11.3 STATISTICAL ANALYSIS PLAN FOR PRIMARY AND SECONDARY OUTCOMES

Initially, descriptive statistics (means, medians, frequency distributions, standard deviations, boxplots, etc.) for all characteristics will be examined for each group. Either parametric or nonparametric statistical (depending on results from the descriptive statistics) tests will be used for comparing results of the randomization. Because recruitment will take place over a long period (projected 3.5 years), descriptive statistics will further be examined in 4-6 month intervals (depending on the frequency of enrollments). This is to check that there are no patterns or differences in the subject characteristics over the enrollment time period. As the trial progresses, these characteristics will be continuously monitored and compared, so at that moment if there are differences in the distributions over time, the study team and the Data Safety Monitoring Board can convene to discuss. Additionally potential covariates, such as, age at entry, sex, weight of subject, time of year, etc., will also be statistically examined using univariate statistical tests.

For testing the primary objective (Aim 1), i.e., comparing the rates of AAD between the BB-12 and control groups, Fisher's Exact Probability test will be used. The relative risk of AAD for BB-

12 versus control and the 95% confidence interval will be calculated to display magnitude of the relationship. If the rates of AAD need to be adjusted for covariates, then multiple logistic regression models will be employed for predicting the adjusted rates of AAD. Covariates will be examined for multi-collinearity so as not to saturate the multiple logistic regression models constructed. With this large number of subjects enrolled, it is not expected that the number of AAD cases will be small enough to warrant further statistical methods. However, if the number of AAD cases is very small then exact statistical testing methods will be exclusively used for making the comparisons and performing any pertinent subgroup analyses. The Pediatric Quality of Life Inventory™ (PedsQL™) has a validated and easy scoring system.[104, 105]

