For Aim 2, numerous exploratory techniques (i.e., all descriptive statistics previously mentioned) will be performed to verify that the probiotic is safe and well tolerated. Additionally, the AEs will be collected and studied over time of enrollment. The rates of AEs will be estimated, 95% confidence interval be constructed for describing precision and statistically compared between groups. This will be accomplished using parametric or nonparametric tests. Further, in order to accurately identify patient populations or subgroups that can benefit from the BB-12 probiotic, decision tree models will be examined. Using decision trees, we may be able to identify groups of subjects that have no AEs versus those with an AE. Similarly, cluster analyses may also be employed to identify potential pockets of subjects that share similar characteristics but differ with respect to AEs. This is related to an area known as "unsupervised" modeling in data mining, but is appropriate in this Phase II trial for finding subgroups of subjects that have plausible similarities and also differences.

Statistical analysis will be performed using the intention to treat principle; all subjects enrolled and randomized will be accounted for in the final analysis in their randomized group. One interim analysis will be performed when approximately 50% of the subjects have been recruited. While the alpha for stopping the trial will be set at 0.01, it is unlikely that we would want to stop this trial at that point even if significance is achieved, but the Data Safety Monitoring Board, PI and NIH representative will make that final decision. For Aim 1, the level of significance for the primary objective will be tested at alpha = 0.029 to account for the one interim analysis.

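### Section 11.2 overstates power: all five figures given after the final alpha is lowered to 0.029 exceed what Fisher's exact test delivers at that level, and three of them match alpha 0.05

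*Combined protocol and SAP*

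**What the plan says.** Section 11.2 starts from 22% diarrhoea on control and 8% on probiotic. With 150 participants in each arm, the design "would provide a power of 0.92 for detecting a difference of 0.14 (0.22 control - 0.08 probiotic) at alpha = 0.05, 2-tailed". It then allows for one interim analysis: "adjusting the final p-value to 0.029, the power would still be 90% for detecting the difference of 0.14". Next it gives 80% power for a difference of 0.12, and "power would be equal to 74% if the final difference in rates were equal to 0.10". For loss to follow-up it says that "if the lost to follow-up rate is as high as 10% (then N=270, approximately 135 per group), power would still be 90" per cent for 0.14, with 80% for 0.12. No alpha is attached to any figure after the sentence that introduces 0.029, and no pair of rates is given for 0.12 or 0.10.

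Section 11.3 sets the analysis. For the primary objective "Fisher's Exact Probability test will be used", and "the level of significance for the primary objective will be tested at alpha = 0.029 to account for the one interim analysis". The interim stopping level is 0.01 at about 50% recruitment. Section 11.2 states that a two-tailed alternative was used.

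**The concern.** The figures conflict on their face: 90% and 80% appear for 300 participants and again for 270. With the test, alpha and rates held fixed, losing 10% of the sample must reduce power. The drop from 80% to only 74% when the difference shrinks from 0.12 to 0.10 also looks too small. Both features suggest that some figures were worked at 0.05 and others at 0.029. In addition, a normal-approximation formula seems to have been used for planning, while the analysis uses Fisher's test, which is conservative.

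At stake is how a null result is read. A reader of section 11.2 would take the type II error to be 10% for the design effect after 10% loss, and 26% for a 10-point effect. An effect near 10 points is not remote: section 4.1.6 cites a paediatric trial with an 11-point difference.

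**Working it through.** **Inputs.** From section 11.2: 22% v 8%, 150 per arm (135 after 10% loss), 1:1 allocation, two-sided. From section 11.3: Fisher's exact test, final alpha 0.029, interim alpha 0.01. The rates behind 0.12 and 0.10 are not given. As an assumption, either the probiotic rate stays at 8% (control 20% or 18%) or the control rate stays at 22% (probiotic 10% or 12%); both are shown.

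**Formula (pooled z-test).** With d = p1 − p2, p̄ the mean rate and n per arm:
- SE0 = √[2p̄(1−p̄)/n]
- SE1 = √{[p1(1−p1) + p2(1−p2)]/n}
- power = Φ[(d − z·SE0)/SE1], with z = 1.960 at alpha 0.05 and 2.1835 at 0.029
- the unpooled version is Φ(d/SE1 − z)

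**The plan's base case, 22% v 8%, n = 150.** SE0 = √(2×0.15×0.85/150) = 0.04123. SE1 = √[(0.1716+0.0736)/150] = 0.04043.
- Alpha 0.05: (0.14 − 1.960×0.04123)/0.04043 = 1.464, power 0.928. Fisher gives 0.914. The stated 0.92 reproduces.
- Alpha 0.029: (0.14 − 2.1835×0.04123)/0.04043 = 1.236, power 0.892; unpooled 0.900. The stated 90% reproduces as a z-test figure.

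**After 10% loss, 22% v 8%, n = 135.** SE0 = 0.04346, SE1 = 0.04262.
- Alpha 0.05: (0.14 − 1.960×0.04346)/0.04262 = 1.286, power 0.901. This matches the stated 90%.
- Alpha 0.029: (0.14 − 2.1835×0.04346)/0.04262 = 1.058, power 0.855. This does not match.

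**Difference 0.10, 18% v 8%, n = 150.** SE0 = 0.03883, SE1 = 0.03840.
- Alpha 0.05: (0.10 − 1.960×0.03883)/0.03840 = 0.622, power 0.733; unpooled 0.740. This matches the stated 74%.
- Alpha 0.029: (0.10 − 2.1835×0.03883)/0.03840 = 0.396, power 0.654.

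**All figures.** Fisher power is the total probability, under two independent binomials, of every table whose two-sided Fisher p-value is at most 0.029.

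| N | Rates | Stated | Pooled z, 0.05 | Pooled z, 0.029 | Fisher, 0.029 |
|---|---|---|---|---|---|
| 300 | 22% v 8% | 90% | 0.928 | 0.892 | 0.871 |
| 300 | 20% v 8% | 80% | 0.853 | 0.795 | 0.757 |
| 300 | 22% v 10% | 80% | 0.812 | 0.745 | 0.703 |
| 300 | 18% v 8% | 74% | 0.733 | 0.654 | 0.598 |
| 300 | 22% v 12% | 74% | 0.636 | 0.549 | 0.495 |
| 270 | 22% v 8% | 90% | 0.901 | 0.855 | 0.833 |
| 270 | 20% v 8% | 80% | 0.815 | 0.748 | 0.710 |
| 270 | 22% v 10% | 80% | 0.770 | 0.696 | 0.653 |

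**Two causes.** The 74% at N=300 and the 90% and 80% at N=270 fit alpha 0.05, not 0.029. The 90% at N=300, and the 80% at N=300 if the rates are 20% v 8%, are sound z-test values at 0.029; they fall short only because Fisher's test is conservative.

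**Credit for the interim look.** Counting rejection at 0.01 at half the sample, simulated Fisher power for 22% v 8% is about 0.875 (N=300) and 0.836 (N=270). Across all scenarios the gain is about 0.3 to 1 point.

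**The case against.** **Not every figure has the wrong alpha.** This is correct. Two of the five are legitimate normal-approximation values at 0.029, and planning with a z formula before a Fisher analysis is common. For those two the gap is 3 to 4 points (with 20% v 8% for the 0.12 difference).

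**The loss-to-follow-up sentence may refer back to alpha 0.05.** It names no alpha. But it follows the 0.029 adjustment and presents the power as maintained, and the primary objective is tested at 0.029 only. Even at 0.05, Fisher gives 0.882 and 0.780 (20% v 8%) at N=270: close to the stated figures, but for a test that will not be the final one.

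**A one-sided reading comes close.** One-sided Fisher at 0.029 gives 0.891 and 0.795 at N=270. Section 11.2 says two-tailed, so this does not rescue the figures.

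**The smaller-difference figures depend on unstated rates.** This stands as a limit. The 74% is matched only by 18% v 8% among the pairs considered, so the like-for-like Fisher value is 0.598; 0.495 belongs to a different scenario. Lower rates in both arms would raise power: by pooled z at 0.029 and N=300, a 10-point difference has 0.762 with 5% on probiotic and 0.723 with 6%. Those same probiotic rates would give 0.877 and 0.849 for 0.12, not the stated 80%, so they do not explain both figures. The 90% at N=270 has no such escape, because its rates are given.

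**The design effect still has more than 80% power, and a confidence interval will be reported.** Both are true. They limit the practical harm for the 14-point difference but do not make the stated figures right.

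**Conclusion.** The concern holds. Under two-sided Fisher at 0.029, all five figures stated after the interim adjustment are too high:
- N=300: about 3 points for 0.14, 4 to 10 for 0.12, and 14 to 25 for 0.10.
- N=270: about 7 points for 0.14 and 9 to 15 for 0.12.

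With 10% loss, the type II error at the design effect is 1 − 0.833, about 17% rather than 10%. For a 10-point difference it is 40% (18% v 8%) to 50% (22% v 12%) rather than 26%.

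The results for 0.14 rest only on the plan's own inputs. Those for 0.12 and 0.10 assume that one of the two planning rates is held fixed. The error is moderate for the planned effect and large for the 10-point effect.

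**What to change.** Restate section 11.2 for Fisher's exact test at final alpha 0.029:
- N=300: 87% (0.14), 70–76% (0.12), 50–60% (0.10).
- N=270: 83% (0.14), 65–71% (0.12).

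Give the test, the alpha and both rates behind every figure; once the rates for the smaller differences are named, each range becomes a single number. The cost is rewording and a less favourable statement of power. No extra participants are needed and the conduct of the trial does not change.

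If the sponsor wants to keep 90%, restating is not enough. These are the options, none of them needed for the correction:
- **Sample size.** Fisher at 0.029 for 22% v 8% needs about 163 per arm, or 326 evaluable; with 10% loss, 326/0.9 = 362.2, so 363 randomised.
- **Test.** Boschloo's exact test keeps the exact size and is uniformly more powerful than Fisher's. At 0.029 it gives 0.893 (N=300) and 0.857 (N=270).
- **Final alpha.** Levels of 0.01 and 0.029 at half and full information spend only about 0.035 overall. A final level near 0.045 would still hold 0.05 overall, and Fisher would then give about 0.91 (N=300) and 0.87 (N=270).

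A change of test or alpha would have to be fixed before anyone sees outcome data by arm.

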11.3 STATISTICAL ANALYSIS PLAN FOR PRIMARY AND SECONDARY OUTCOMES

Initially, descriptive statistics (means, medians, frequency distributions, standard deviations, boxplots, etc.) for all characteristics will be examined for each group. Either parametric or nonparametric statistical (depending on results from the descriptive statistics) tests will be used for comparing results of the randomization. Because recruitment will take place over a long period (projected 3.5 years), descriptive statistics will further be examined in 4-6 month intervals (depending on the frequency of enrollments). This is to check that there are no patterns or differences in the subject characteristics over the enrollment time period. As the trial progresses, these characteristics will be continuously monitored and compared, so at that moment if there are differences in the distributions over time, the study team and the Data Safety Monitoring Board can convene to discuss. Additionally potential covariates, such as, age at entry, sex, weight of subject, time of year, etc., will also be statistically examined using univariate statistical tests.

For testing the primary objective (Aim 1), i.e., comparing the rates of AAD between the BB-12 and control groups, Fisher's Exact Probability test will be used. The relative risk of AAD for BB-

12 versus control and the 95% confidence interval will be calculated to display magnitude of the relationship. If the rates of AAD need to be adjusted for covariates, then multiple logistic regression models will be employed for predicting the adjusted rates of AAD. Covariates will be examined for multi-collinearity so as not to saturate the multiple logistic regression models constructed. With this large number of subjects enrolled, it is not expected that the number of AAD cases will be small enough to warrant further statistical methods. However, if the number of AAD cases is very small then exact statistical testing methods will be exclusively used for making the comparisons and performing any pertinent subgroup analyses. The Pediatric Quality of Life Inventory™ (PedsQL™) has a validated and easy scoring system.[104, 105]

For Aim 2, numerous exploratory techniques (i.e., all descriptive statistics previously mentioned) will be performed to verify that the probiotic is safe and well tolerated. Additionally, the AEs will be collected and studied over time of enrollment. The rates of AEs will be estimated, 95% confidence interval be constructed for describing precision and statistically compared between groups. This will be accomplished using parametric or nonparametric tests. Further, in order to accurately identify patient populations or subgroups that can benefit from the BB-12 probiotic, decision tree models will be examined. Using decision trees, we may be able to identify groups of subjects that have no AEs versus those with an AE. Similarly, cluster analyses may also be employed to identify potential pockets of subjects that share similar characteristics but differ with respect to AEs. This is related to an area known as "unsupervised" modeling in data mining, but is appropriate in this Phase II trial for finding subgroups of subjects that have plausible similarities and also differences.

Statistical analysis will be performed using the intention to treat principle; all subjects enrolled and randomized will be accounted for in the final analysis in their randomized group. One interim analysis will be performed when approximately 50% of the subjects have been recruited. While the alpha for stopping the trial will be set at 0.01, it is unlikely that we would want to stop this trial at that point even if significance is achieved, but the Data Safety Monitoring Board, PI and NIH representative will make that final decision. For Aim 1, the level of significance for the primary objective will be tested at alpha = 0.029 to account for the one interim analysis.

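### Fisher's exact test at 0.029 is valid but conservative: the stated 90% power is about 87% with exactly equal arms and 88–89% with slightly unequal ones, and Boschloo's test would recover part of the loss

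*Combined protocol and SAP*

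**What the plan says.** Section 11.3 names the primary test: for "comparing the rates of AAD between the BB-12 and control groups, Fisher's Exact Probability test will be used". It also sets the levels. For the interim look at about half of recruitment it says "While the alpha for stopping the trial will be set at 0.01", and for the final analysis "the level of significance for the primary objective will be tested at alpha = 0.029 to account for the one interim analysis".

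Section 11.2 gives the planning figures. It says that "a total sample of 300 subject (150 per group) would provide a power of 0.92". The rates behind that figure are 0.22 under control yogurt and 0.08 under probiotic yogurt, tested two-sided at 0.05. It then says that after "adjusting the final p-value to 0.029, the power would still be 90% for detecting the difference of 0.14 in the rates of AAD". It describes the calculation as two-sided: "we still used a two-tailed alternative for estimating the sample size in order to be conservative". It also considers a 10% loss to follow-up, leaving about 135 per group.

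Section 11.2 does not say which test or formula produced the power figures. Neither section mentions that Fisher's test is conservative, and neither names an unconditional exact test.

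**The concern.** Fisher's test conditions on the total number of cases. Because the counts are discrete, the conditional p-value can take only certain values, so the test usually rejects less often under the null than its nominal level allows. Here the nominal level has already been lowered to 0.029 for the interim look, and part of what remains goes unused.

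Two things follow. The power stated in 11.2 may not be the power of the test named in 11.3. And the trial may accept a somewhat lower chance of detecting a real effect than its own error limit requires. Nothing in 11.3 suggests that sparse data force the choice. It expects enough cases, and the planning rates imply 150 × 0.22 + 150 × 0.08 = 33 + 12 = 45.

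**Working it through.** **Inputs.** Control rate 0.22, probiotic rate 0.08, 150 per arm, about 135 per arm after 10% loss (11.2). Fisher's test, final level 0.029, interim level 0.01 (11.3). The test is taken as two-sided, as in the sample size section; 11.3 does not state this.

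**1. The plan's own figure.** Normal approximation with pooled rate 0.15:
- standard error under the null: √(2 × 0.15 × 0.85 / 150) = 0.0412
- standard error under the alternative: √((0.22 × 0.78 + 0.08 × 0.92) / 150) = 0.0404
- level 0.05: Φ((0.14 − 1.960 × 0.0412) / 0.0404) = 0.928 (stated 0.92)
- level 0.029, pooled: Φ((0.14 − 2.183 × 0.0412) / 0.0404) = 0.892
- level 0.029, unpooled: Φ(0.14 / 0.0404 − 2.183) = 0.900 (stated 0.90)

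The stated 90% is therefore what a normal approximation gives.

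**2. Size and power of the named test.** For every pair of counts (x, y), take the two-sided Fisher p-value, which is the sum of the table probabilities no larger than the observed one. Then

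P(reject) = Σ Σ Bin(x; n₁, p₁) Bin(y; n₂, p₂) · 1{Fisher p ≤ 0.029}.

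Setting p₁ = p₂ gives the size. At 150 v 150 it is 0.0177, 0.0190, 0.0202 and 0.0212 at common rates of 8%, 15%, 22% and 30%. Setting the rates to 0.22 and 0.08 gives a power of 87.1%. At level 0.05 the same calculation gives 91.4%, close to the stated 0.92, so the shortfall shows mainly at 0.029.

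**3. Boschloo's test.** It uses the Fisher p-value as its statistic. The cut-off is the largest value whose rejection probability stays at or below 0.029 at every common rate. At 150 v 150 the cut-off is 0.0364 and the maximum size is 0.0289. Since the cut-off exceeds 0.029, every table that Fisher's test rejects is also rejected, so power cannot fall.

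**4. Results for 0.22 v 0.08.** Ranges show which arm is the larger.

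| Analysed arms | Fisher size at 15% | Fisher power | Boschloo power |
|---|---|---|---|
| 150 v 150 | 0.0190 | 87.1% | 89.3% |
| 149 v 151 | 0.0231 | 88.1–89.1% | 88.9–90.4% |
| 148 v 152 | 0.0239 | 88.8–89.0% | 89.8% |
| 135 v 135 | 0.0196 | 83.3% | 85.7% |
| 134 v 136 | 0.0239 | 84.4–85.8% | 85.6–86.9% |

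The unused share of the level at a 15% rate is 1 − 0.0190/0.029 = 34% at 150 v 150, but 1 − 0.0231/0.029 = 20% at 149 v 151.

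**5. Smaller differences.** At 150 v 150, Fisher to Boschloo: 0.20 v 0.08, 75.7% to 79.0%; 0.22 v 0.10, 70.3% to 74.0%; 0.22 v 0.12, 49.5% to 53.7%. At 149 v 151, 0.22 v 0.12 goes from 53.0% to 55.8% in the more favourable direction.

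**6. Both looks together.** Simulating 75 per arm at 0.01 and then 150 per arm at 0.029, with a common rate of 15%, the overall error is about 0.022 with Fisher's test at both looks. It is about 0.028 with Fisher at the interim and Boschloo at the end, and about 0.030 with Boschloo at both. All are well below 0.05.

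**The case against.** The strongest reply is that nothing is invalid. Fisher's test is named in advance, controls the error at 0.029 and is familiar to every reader; preferring another exact test is a choice about efficiency. That stands.

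The second reply is that the loss depends on exact balance, and this also stands. Section 6 promises equal allocation, but 7.4 uses permuted blocks of varying size and 11.2 expects some children with unknown outcome, so exactly equal analysed arms are unlikely. Moving a single child between arms raises Fisher's power from 87.1% to 88.1–89.1%. A reader might infer from the equal-arm figures that a third of the level is always wasted, or that the choice of test costs 2–4 points whatever happens. Neither holds once the arms differ by a few children. A reader might also convert the loss into extra children, since Fisher's test at 158 per arm reaches Boschloo's 89.3%. That equivalence belongs to exact balance and should not be used.

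Pearson's chi-square test gives 90.5% at 150 v 150, which might suggest it as the benchmark. It is not a fair one: its maximum size is 0.0325, above 0.029.

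Finally, the current version is dated July 2021 and the documents do not say whether the interim look has taken place. A change at that look may no longer be open.

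**Conclusion.** The point holds as a cheap improvement in efficiency. For the test actually named, power at 0.22 v 0.08 is 87.1% at 150 v 150, about 88–89% at 149 v 151 or 148 v 152, and about 83–86% near 135 per arm. The 90% in 11.2 is not clearly met.

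Boschloo's test recovers about 2 points at the planned difference and about 3–4 points at smaller ones if the arms are exactly equal. With slightly unequal arms the gains are about 1–1.5 points and roughly 1–3 points. Its maximum size stays at or below 0.029 throughout.

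The sizes rest on the planning rates in 11.2, a two-sided test, and a common rate near 15% for the quoted error rates. The direction does not depend on them. A reader might infer an error-rate violation, or a change that costs nothing. The first is wrong, because Fisher's test errs on the safe side. The second overstates the case: the actual error rate rises, though within the limit, and the test is less familiar.

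**What to change.** Before unblinding, name Boschloo's unconditional exact test in 11.3 as the primary test, two-sided, at the existing final level of 0.029. Use it at the interim level of 0.01 as well if that look has not yet taken place. Report Fisher's test as a sensitivity result. The sample size and the two levels stay as they are.

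In 11.2, restate the power for the test that is named and at 0.029, including the case of about 135 per group, and say how it was computed. If the sponsor prefers to keep Fisher's test, restate the 90% as about 87% for exactly equal arms and 88–89% for slightly unequal ones.

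The cost is a line in 11.3 and a revised power statement in 11.2. No children are added, and standard software has the test. The downside is that readers know it less well than Fisher's, which the sensitivity result eases.

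### The primary relative risk is to be reported with a 95% interval although its test is run at 0.029, so the interval can exclude 1 when the test has failed

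*Combined protocol and SAP*

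**What the plan says.** Section 11.3 of the combined protocol and SAP names Fisher's test for comparing the rates of antibiotic-associated diarrhea ("Exact Probability test will be used"). It then adds the relative risk, for which "the 95% confidence interval will be calculated to display magnitude of the relationship". No interval method is named.

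The same section sets the final level: the primary objective "will be tested at alpha = 0.029 to account for the one interim analysis". At the interim look, "the alpha for stopping the trial will be set at 0.01". Section 11.2 uses the same final figure ("adjusting the final p-value to 0.029").

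On sidedness, section 11.2 bases its first power figure on "detecting a difference of 0.14 (0.22 control - 0.08 probiotic) at alpha = 0.05, 2-tailed". It calls the hypothesis one-sided, but says "we still used a two-tailed alternative for estimating the sample size in order to be conservative". Section 11.3 does not state the sidedness of the final test.

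The documents give no interim-adjusted interval. They also do not say how to read the 95% interval if it disagrees with the test.

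**The concern.** The interim adjustment is applied to the primary p-value but not to the interval printed beside it. A result with p between 0.029 and 0.05 fails the primary test, yet its 95% interval can exclude 1. Many readers take an interval that excludes 1 as a positive finding, so the same results table would point two ways. The conflict is most likely when the true effect is smaller than the planning value, including the differences of 0.12 and 0.10 that section 11.2 itself considers. If the interval level were chosen only after such a p-value had been seen, the choice would look post hoc.

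**Working it through.** **Inputs.** From section 11.2: 150 per group, 1:1, rates 0.22 v 0.08, smaller differences of 0.12 and 0.10, two-tailed calculation. From sections 11.2 and 11.3: final level 0.029. From section 11.3: Fisher's exact test and a 95% interval for the relative risk. Assumed: a log-Wald interval, and, for the smaller differences, a control rate held at 0.22.

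**1. The plan's own power figures.** Normal approximation with pooled variance, n = 150 and mean rate 0.15:

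- Power = Φ[(0.14·√150 − z·√(2·0.15·0.85)) / √(0.22·0.78 + 0.08·0.92)] = Φ[(1.715 − 0.505z)/0.495].
- At 0.05, z = 1.960: Φ(1.464) = 0.928. The plan states 0.92.
- At 0.029, z = 2.183: Φ(1.236) = 0.892. The plan states 90%.

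The figures reproduce to within about a point, which supports reading 0.029 as a two-sided level. Exact Fisher power by enumeration is 0.914 and 0.871.

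**2. The level that matches the test.** 1 − 0.029 = 97.1%. The multiplier ratio is 2.183/1.960 = 1.11, so the level change alone makes the interval about 11% wider on the log scale.

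**3. Single tables.** With x BB-12 events and 33 control events (0.22 × 150):

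- ln RR = ln(x/33); SE = √(1/x + 1/33 − 2/150); limits = exp(ln RR ± z·SE).
- x = 19: ln RR = −0.552, SE = 0.264.
- x = 18: ln RR = −0.606, SE = 0.269.

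| Events | RR | Two-sided Fisher p | 95% CI | 97.1% CI |
|---|---|---|---|---|
| 17 v 33 | 0.515 | 0.0195 | 0.300–0.884 | 0.282–0.940 |
| 18 v 33 | 0.545 | 0.031 | 0.322–0.925 | 0.303–0.982 |
| 19 v 33 | 0.576 | 0.047 | 0.343–0.966 | 0.324–1.024 |
| 20 v 33 | 0.606 | 0.069 | 0.365–1.006 | 0.344–1.066 |

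The tables with 18 and 19 events fail at 0.029 while their 95% intervals exclude 1. A 97.1% log-Wald interval resolves 19 v 33 but not 18 v 33.

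**4. How often this happens.** All 2×2 outcomes with 150 per group were enumerated under independent binomials. Conflict means that the interval excludes 1 while Fisher p exceeds 0.029. The part due to level is the probability that p lies above 0.029 and at or below 0.05; the 95% interval excluded 1 in all of that probability. The remainder has p above 0.05, where log-Wald and Fisher disagree even at a common 0.05 level.

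| True rates | Conflict, 95% CI | Due to level | Log-Wald v Fisher | Conflict, 97.1% log-Wald |
|---|---|---|---|---|
| 0.22 v 0.08 | 6.0% | 4.3% | 1.7% | 2.2% |
| 0.22 v 0.10 | 10.7% | 7.2% | 3.5% | 3.6% |
| 0.22 v 0.12 | 13.6% | 8.6% | 5.0% | 4.2% |
| 0.22 v 0.22 | 2.7% | 1.6% | 1.1% | 0.6% |

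The reverse conflict, with p at or below 0.029 and a 95% interval that includes 1, had probability 0.000 in every scenario. The disagreement therefore always favours a positive impression.

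**5. With 10% loss (135 per group).** The first column becomes 7.1%, 11.3%, 13.1% and 2.6%. With 30 control events, the conflict occurs at 16 BB-12 events (p = 0.035, 95% CI 0.305–0.932) and at 17 (p = 0.053, 0.329–0.977).

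**The case against.** The strongest reply is that the plan contains one decision rule. Section 11.3 tests at 0.029 and gives the interval a separate job, which is to show magnitude. A reader might infer that the trial has two competing criteria for success, or that its type I error is inflated. The documents support neither: nothing makes success depend on the interval, and the error rate of the formal test is untouched. That part of the reply stands and limits the weight of the point. It does not remove it, because the plan never says that the interval is not for inference.

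A reader might also put the whole of the 6% to 14% down to the 0.029 level. That would overstate it. Roughly 28% to 37% of the conflict comes from pairing an assumed log-Wald interval with Fisher's conservative test, and would remain at a common 0.05 level.

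The example also depends on sidedness. One-sided, 19 v 33 gives p = 0.023, which passes 0.029. Two-sided is the natural reading because the power calculation is two-tailed, but that choice is tied in words to the sample size only. Section 11.3 should settle it.

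Finally, 0.029 is stricter than an overall 0.05 requires. With 0.01 at half the information and 0.029 at the end, the overall two-sided level is about 0.035. This does not weaken the point; it means that the interval level should be tied to the final alpha and not fixed at 97.1%. The matching proposed here covers the final analysis only, not a stop at the interim look.

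**Conclusion.** The point holds as a reporting inconsistency that is worth correcting. At the planned size, the primary interval would exclude 1 beside a failed primary test in about 6% of trials at the planning rates, 11% to 14% at differences of 0.12 and 0.10, and 2.7% with no effect. The mismatch of levels alone contributes 4.3%, 7.2%, 8.6% and 1.6%. These figures assume a log-Wald interval, a two-sided Fisher test, 150 per group and a control rate of 0.22. The size and the decision rule of the trial stand as they are; what needs correcting is how the primary result will be presented and read.

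**What to change.** Amend section 11.3, before unblinding, to state that:

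- the final Fisher test is two-sided at the final alpha, in line with the two-tailed calculation in section 11.2;
- the relative risk is reported with a 1 − alpha interval (97.1% at 0.029) obtained by inverting that same exact test, and the level follows any revision of the final alpha;
- any 95% interval also shown is descriptive and not for inference.

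The construction should be named. Fisher's test inverts most directly to an odds ratio, and default exact intervals in software need not match the two-sided Fisher p-value. The requirement to write down is that the interval for the relative risk excludes 1 exactly when Fisher p is at or below the final alpha. Changing a log-Wald interval from 95% to 97.1% is not enough, as 18 v 33 shows.

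The cost is a few lines of text and a wider interval: about 11% on the log scale from the level, and somewhat more from exact inversion. Sample size and trial conduct do not change.
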